#### **6.4      Evaluable subject**

**Evaluable for response:** Any subject who receives at least 80% of ONC201 doses during the first two cycles of treatment (i.e., at least 9 doses of ONC201) and have at least one disease re-evaluation will be evaluable for response. Dose reductions will not be included in this 80%, just number total doses taken will be included.

**Evaluable for toxicity:** Any subject who receives at least one dose of treatment on this protocol should be evaluable for toxicity. Safety will be assessed by NCI CTCAE v5.0.

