### **5.2 ONC201 administration**

The study drug, ONC201, will be supplied in capsule form for oral dosing. ONC201 625 mg (5 tablets of 125 mg each) will be given by mouth on Days 3 and 4 of each week for each cycle (administered on days 3,4, 10,11 and 17,18). Treatment will be administered primarily on an outpatient basis, but can be administered as an inpatient. A cycle is equal to 21 days.

Subjects should take the dose of ONC201 specified by their physician 2 hours prior or 2 hours following food or a meal. If the subject vomits after taking ONC201, they should not retake the dose. Missed doses will not be made up, if more than 1 day pass from the intended day of administration.

ONC201 should be taken with a glass of water and consumed over as short a time as possible. Subjects should swallow the capsules as a whole and not chew them. Do not crush or empty the capsule. If vomiting occurs during the course of treatment, no re-dosing of the subject is allowed before the next scheduled dose. The occurrence and frequency of any vomiting during a treatment cycle must be noted as an adverse event.

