### **5.3 Methionine-restricted diet**

Under the supervision of a registered dietitian (either at the site or from the coordinating site) and the site investigator, subjects will receive an individualized dietary prescription that incorporates a methionine-free amino acid-modified

medical food (Hominex-2, Abbott Nutrition) supplemented with low-methionine foods (**Table 2**). Hominex-2 contains a mixture of L-amino acids but lacks methionine. Subjects will be instructed by the dietitian in the preparation of Hominex-2 shakes to deliver 100% of daily protein requirements (0.8 g/kg/day) and 75% of the caloric requirements. The remaining calories will be met with low-methionine foods, including fruits, vegetables, grains (*e.g.*, specified cereal and bread), margarine and cooking oils. Subjects will be provided with a list of foods that are low in methionine. Calories will not be restricted. Subjects will be encouraged to follow their usual level of physical activity and instructed to maintain a daily diet and exercise diary that will be reviewed by the dietitian. Subjects will take the MR diet days 1 through 5 of each week (defined as a 7-day period) while taking the ONC201. Subjects may resume a general diet on days 6 and 7 each week. Phase I and phase II trials of a methionine-free diet alone or in combination with chemotherapy in subjects with metastatic or recurrent solid tumors have confirmed the safety and tolerability of methionine deprivation (up to 39 weeks)[24, 25].

A 24-hour dietary recall exercise [40] will be completed by a dietitian prior to starting the methionine restricted diet during cycle 1. The recall and food diaries will be analyzed using Food Processor® Nutrition and Fitness Software, ESHA Research, Salem, OR, USA. Food intake will be entered in and a report detailing the nutritional components of the food taken will be generated and provided back to the dietitian. Gender, age, height and weight will be entered for use with the analysis of the diet taken. This dietary analysis will not be provided to the subjects.

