**Table 2: Methionine-restricted diet shakes**

Regimen Description					
Agent	Premedications; Precautions	Dose	Route	Schedule	Cycle Length
Methionine-free amino acid- modified medical food	None	shakes	Oral	Per dietitian recommendation	Days 1 through 5* of every 7- day period. Cycle = 21 days

\*Subjects should follow the methionine restricted diet for days 1-5 of every 7-day period. However, 1 day of methionine restriction may be skipped in this 5-day restriction period if needed to allow flexibility around holidays, vacations, etc. The 4-5 days of the diet during each 7-day period must be consecutive. The diet must be

followed for a minimum of 24 hours prior to the collection of CTCs and for a minimum of 24 hours prior to dosing with ONC201.

The subject will be requested to maintain a medication diary of each dose of medication. The medication diary (one for ONC201 and for the shakes) and the diet/exercise diary will be returned to clinic staff at the end of each cycle of therapy. It will not be a deviation if the subject isn't able to complete the diet/exercise diary. Subjects will meet with the dietitian on day 1 of cycles 1 and 2 to review the diet/exercise diary. Additionally, the dietitian will contact the subject during the initial week of cycle 1 to assess tolerance of the diet and to address questions the subjects may have. Subjects will be able to contact the dietitian during normal business hours to discuss dietary questions or concerns related to the study.

Recipes for the methionine restricted shakes will be developed to fit the needs of individual subjects (taste preferences, energy needs, etc.).

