### **13.3 Analysis datasets**

Population	Definition
Evaluable for Safety	This will comprise all subjects who receive at least one dose of trial drug and either undergo at least one post-baseline assessment or die before any evaluation.
Evaluable for Efficacy	This will comprise all subjects who receive at least 80% of ONC201 + MR diet doses during the first two cycles of treatment (i.e., at least 9 doses of ONC201) and have at least one disease re-evaluation. Subjects who are not evaluable for response, however, will be replaced.

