### **13.6 Assessment of efficacy**

All subjects who have received at least 80% of ONC201 + MR diet during the first two cycles of treatment and have their disease re-evaluated will be evaluable for assessment of objective response.

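### The evaluability rule equates 80% of ONC201 doses with 9 doses, which is 75% of the 12 scheduled, and leaves unclear whether diet adherence counts

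*Combined protocol and SAP*

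**What the plan says.** Section 5.2 has ONC201 "administered on days 3,4, 10,11 and 17,18" of a 21-day cycle, and the study calendar agrees (days 3 and 4, weekly).

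Three sections define who is evaluable for response:

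- Section 6.4: a subject who "receives at least 80% of ONC201 doses during the first two cycles of treatment (i.e., at least 9 doses of ONC201") and has at least one disease re-evaluation. Dose reductions are ignored: "just number total doses taken will be included". Diet is not mentioned.
- Section 13.3: a subject who receives "at least 80% of ONC201 + MR diet doses during the first two cycles of treatment (i.e., at least 9 doses of ONC201") and has at least one re-evaluation. The diet is named, but the only count is for ONC201. The section adds: "Subjects who are not evaluable for response, however, will be replaced".
- Section 13.6: "All subjects who have received at least 80% of ONC201 + MR diet during the first two cycles of treatment" and have been re-evaluated. There is no count and no unit.

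On the diet, section 5.3 says: "Subjects will take the MR diet days 1 through 5 of each week (defined as a 7-day period) while taking the ONC201". The note to Table 2 adds that "1 day of methionine restriction may be skipped in this 5-day restriction period if needed". Section 5.4 has subjects record the number of shakes. Section 6.1 allows a subject to stop the diet and stay on ONC201.

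**The concern.** There are two faults in one rule. First, the percentage and the count are presented as the same thing and are not. Second, the three sections do not describe the population in the same terms: one counts ONC201 alone, and two name the diet without defining a diet dose or a base for the 80%.

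The rule does more than label an analysis set. Under 13.3 it decides who is replaced, and so who makes up the 13 subjects of stage 1 and the 34 overall. Section 13.2 stops the trial at 1 or fewer responses in 13 and rejects the combination at 5 or fewer in 34, so 2 of 13 and 6 of 34 are needed to pass, and single subjects can decide either look. In an open-label, single-arm trial, a reading settled after responses are known is open to the charge that it was chosen for its result.

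**Working it through.** **ONC201 count.** Inputs: dosing days 3, 4, 10, 11, 17 and 18 of each cycle (5.2); two cycles (6.4, 13.3).

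- Scheduled doses: 6 × 2 = 12.
- 80% of 12 = 9.6, so the smallest whole number that is at least 80% is 10.
- 9/12 = 75.0%; 10/12 = 83.3%.

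The plan's figure of 9 appears only if 9.6 is truncated, which contradicts a minimum of 80%. Nine would be right for 11 scheduled doses (9/11 = 81.8%), but no section schedules 11. Dose reductions cannot explain the gap, because 6.4 counts doses taken whatever their size.

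A subject with exactly 9 doses has missed 3 of 12. A one-week hold (2 doses) plus one other missed dose is enough.

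**Diet.** The wording side by side:

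| Section | Agent named | Count or unit |
|---|---|---|
| 6.4 | ONC201 | 9 doses |
| 13.3 | ONC201 + MR diet | doses, explained only as 9 ONC201 doses |
| 13.6 | ONC201 + MR diet | none |

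Take a subject who meets the ONC201 requirement, has a re-evaluation, and follows little of the diet in the first two cycles. She is evaluable under 6.4. If diet is judged separately, she is not evaluable under 13.3 and is replaced.

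If the unit were days, the base would matter. Scheduled days are 5 × 3 × 2 = 30, and 80% of 30 is 24. A subject who uses every permitted skip has 4 × 6 = 24 days, exactly 80.0%; one more missed day gives 23/30 = 76.7%. If permitted skips were taken out of the base, it would be 24; 80% is then 19.2, so 20 days suffice. No section states either base. If the unit were shakes, no base can be derived, because shakes are individualised.

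**Effect on the Simon rule.** The rule is n1 = 13, continue if more than 1 respond; n = 34, pass if more than 5 respond. The exact binomial chance of passing is the sum over x = 2 to 13 of P(X1 = x) × P(X2 ≥ 6 − x), with X1 ~ Bin(13, p) and X2 ~ Bin(21, p).

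The stated design reproduces: 0.0957 at p = 0.10 (plan: type I error 10%) and 0.8108 at p = 0.25 (plan: power 80%).

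For replacement, let f be the share of subjects in dispute and k their response rate relative to the overall rate. Neither is in the documents; both are assumed. The response rate among counted subjects is then p(1 − fk)/(1 − f). With f = 5% and p = 0.10:

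- k = 0.5: 0.10 × 0.975/0.95 = 0.1026; chance of passing 0.1051.
- k = 1: 0.1000; chance 0.0957, no change.
- k = 1.5: 0.10 × 0.925/0.95 = 0.0974; chance 0.0868.

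For 34 counted subjects, f = 5% means 34 × 0.05/0.95 = 1.8 disputed subjects. The range over f, with disputed subjects replaced:

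| f | p = 0.10: k = 0.5 | p = 0.10: k = 1.5 | p = 0.25: k = 0.5 | p = 0.25: k = 1.5 |
|---|---|---|---|---|
| 2.5% | 0.100 | 0.091 | 0.820 | 0.801 |
| 5% | 0.105 | 0.087 | 0.829 | 0.791 |
| 10% | 0.116 | 0.078 | 0.848 | 0.766 |

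**The case against.** The strongest reply concerns the diet. Section 13.3 explains its own phrase by 9 ONC201 doses, the same count as 6.4, and 13.6 can be taken as a shortened restatement. On that reading the three sections mean the same population and diet does not count. This stands as a possible reading. A reader might infer that 6.4 and 13.3 flatly contradict each other on diet; the documents do not support that. What remains is ambiguity: the diet is named in two of the three definitions, its role is not stated, and 13.6 lacks even the count that would settle it.

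On the dose count, staff would probably apply 9, since it is printed twice. That is fair, but no text ranks the count above the percentage, and 13.6 carries only the percentage.

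The disputed group is also likely to be small. For doses it is only subjects with exactly 9. For diet it is those with low adherence in the first two cycles who still meet the ONC201 requirement; later diet stops do not matter, and section 6.3 ends protocol therapy altogether for grade 2 or higher weight loss. This limits the likely effect without removing it, given the tight cut-offs.

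Finally, a reader might infer that replacement inflates the type I error above 10%. The documents do not support that either. The direction depends on how disputed subjects respond: the chance of passing rises if they respond less often than the others and falls if they respond more often.

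**Conclusion.** The arithmetic fault is certain: 9 of 12 is 75.0%, and at least 80% requires 10 doses. It stands in both 6.4 and 13.3. The diet point is a real ambiguity, not an established contradiction; its consequence, evaluable under 6.4 but replaced under 13.3, holds only if diet is judged separately.

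The effect on the trial's conclusion cannot be sized from the documents. The Simon figures are illustrations that rest on assumed f and k and on a true response rate defined over disputed and other subjects together. Nothing changes if disputed subjects respond like the others, or if the null hypothesis is defined on the evaluable set. The sample size and cut-offs are sound as stated.

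The rule should be fixed because it governs replacement and the repair is cheap. Whether replaced subjects enter the ORR denominator (9.8.5, 13.7.1) is a separate question that this point does not rest on.

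**What to change.** Before responses are tallied:

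1. In 6.4 and 13.3, state one percentage with its matching count: 80% with at least 10 of 12 doses, or 75% with at least 9 of 12. The choice is the sponsor's.
2. Use one identical definition in 6.4, 13.3 and 13.6 that says whether diet adherence counts.
3. If it counts, say whether it is judged separately from ONC201, name a unit the trial already records, give the base (for days, 30 scheduled or 24 after permitted skips), and state how missing diary entries are treated.

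If diet is not counted, the cost is wording in three sections. If it is counted, there is a small practical burden: shakes have no protocol-wide scheduled number, and section 5.3 does not treat an incomplete diet diary as a deviation, so the unit must be one the records can support.

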#### **6.5      Protocol discontinuation**

If a subject decides to withdraw from the study (and not just from protocol therapy) all efforts should be made to complete and report study assessments as thoroughly as possible until the date of withdrawal. The treating investigator should contact the subject or a responsible relative by telephone to establish as completely as possible the reason for the study withdrawal. A complete final evaluation at the time of the subject's study withdrawal should be made with an explanation of why the subject is withdrawing from the study. If the reason for removal of a subject from the study is an adverse event, it will be recorded on the eCRF.

#### **6.6      Criteria for Early Trial Termination**

Early trial termination will occur if any of the following are met:

- a. Incidence or severity of adverse drug reactions in this or other studies using this drug that indicates a potential health hazard to subjects.
- b. Plans to modify or discontinue the study drug (ONC201), such that the original study drug is no longer provided by the sponsor.

- c. Financial support of the study is withdrawn such that protocol activities can no longer be conducted.
- d. If enrollment or subject withdrawal will impact the ability of the study to meet the stated objectives.
- e. UWCCC Data Safety Monitoring Committee recommendation based on review of required study documents (outlined in section 12).

## 7. STUDY CALENDARS AND EVALUATIONS

Cycle = 21 days	Screening	Cycle 1	Cycle 2	Odd # cycles Begin at Cycle 3	Even # cycles Begin at Cycle 4	End of Treatment	Long-term Follow-up
	-28 days	Day 1 +/- 2 days	Day 1 +/- 2 days	Day 1 +/- 2 days	Day 1 +/- 2 days	35 days from last dose of study treatment +/- 5 days	Every 3 months (+/- 7 days) for 2 years from EOT
Informed consent	X						
Medical history	X						
Diagnosis and staging	X						
Physical Exam	X	X 	X	X	X	X	
Vital signs, wt, waist circumference  , ECOG performance status	X	X 	X	X	X	X	
AEs & concomitant medications, drug diary review 	X	X	X	X	X	X	
LABORATORY ASSESSMENTS							
CBC with differential (minimum to include: Hgb, WBC, Plt, ANC)	X	X 	X	X	X	X	
CMP 	X	X 	X	X	X	X	
Blood for metabolic indices 		X	X		X	X	
Homocysteine/cysteine 		X		X		X	

Cycle = 21 days	Screening	Cycle 1	Cycle 2	Odd # cycles Begin at Cycle 3	Even # cycles Begin at Cycle 4	End of Treatment	Long-term Follow-up
	-28 days	Day 1 +/- 2 days	Day 1 +/- 2 days	Day 1 +/- 2 days	Day 1 +/- 2 days	35 days from last dose of study treatment +/- 5 days	Every 3 months (+/- 7 days) for 2 years from EOT
Pregnancy test (serum) 	- 7 days	X 					
Diet/Exercise Diary		X	X	X	X		
24 Hour Dietary Recall Form		X					
DISEASE ASSESSMENTS							
CT chest, CT or MRI of abdomen and pelvis 	X				X 		X
MRI brain	X 						
Bone scan	X 				X 		
TREATMENT EXPOSURE							
ONC201		Days 3 and 4, weekly	Days 3 and 4, weekly	Days 3 and 4, weekly	Days 3 and 4, weekly		
MR diet		Days 1 - 5 weekly	Days 1 - 5 weekly	Days 1 - 5 weekly	Days 1 - 5 weekly		
CORRELATIVE STUDIES (SPECIMEN COLLECTION)							
Archival Tissue 	X						
Circulating tumor cells		X 	X 			X 	
Plasma methionine & methionine metabolites		X 	X 		X 	X 	
FOLLOW-UP							
Survival							X

- (1) Blood will be taken to assess metabolic indices at baseline, cycle 2 day 5, then day 5 of every other cycle, and at end of treatment. Indices are fasting: glucose, insulin, IGF-1, and leptin levels. If necessary, these labs may be drawn as early as day 2, but prefer to be as close to day 5 as possible without going over.
- (2) Blood will be taken to assess plasma methionine levels at baseline, cycle 2 day 5, then day 5 of every other cycle, and at end of treatment. Subjects must be fasting. If necessary, these labs may be drawn as early as day 2, but prefer to be as close to day 5 as possible without going over.
- (3) If clinically indicated.
- (4) Optional biopsy prior to study entry.
- (5) Blood for circulating tumor cells will be taken at baseline, day 5 of cycle 2, and at end of treatment. If necessary, these labs may be drawn as early as day 2, but prefer to be as close to day 5 as possible without going over.
- (6) For women of childbearing potential. To be completed within 7 days of randomization. Must be repeated at cycle 1 day 1 if not completed in previous 7 days.
- (7) Subjects whose treatment is interrupted or permanently discontinued due to an adverse event (including lab values) should be followed per section 11.1.1.
- (8) Waist circumference, optional if not possible due to site limitations. Not required at screening.
- (9) CMP to include sodium, potassium, chloride, carbon dioxide, glucose, BUN, creatinine, calcium, albumin, total protein, alkaline phosphatase, aspartate aminotransferase (AST), alanine aminotransferase (ALT), and total bilirubin.
- (10) CT chest with or without contrast and CT with contrast or MRI of Abdomen/Pelvis to be completed during screening and  $\leq$  7 days prior to every third cycle starting at cycle four (approximately every 9 weeks; e.g. cycles 4, 7, 10, etc.). If subjects discontinue study treatment prior to disease progression, scans during follow-up will be completed per standard of care, but RECIST measurements must be completed until disease progression or start of new anti-cancer therapy.
- (11) Homocysteine/cysteine level at: baseline and every 3 cycles while on study (C1, C4, C7, etc.) and at end of treatment.
- (12) One block or 10 unstained slides.
- (13) labs/physical exam/ECOG PS does not need to be repeated if done within 7 days prior to C1D1

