### **2.2 Secondary Objectives:**

2.2.1 To determine progression-free survival (PFS) to ONC201 with a methionine-restricted diet in patients with metastatic TNBC.

2.2.2 To determine clinical benefit rate (complete and partial response plus stable disease) (CBR) at 4 months to ONC201 with a methionine-restricted diet in patients with metastatic TNBC.

2.2.3 To determine overall survival (OS) to ONC201 with a methionine-restricted diet in patients with metastatic TNBC.

2.2.4 To determine the safety of adding a methionine-restricted diet to ONC201 in patients with metastatic TNBC

2.2.4 To assess metabolic indices in patients with metastatic TNBC treated with ONC201 and a methionine-restricted diet.

2.2.5 To assess the expression of TRAIL receptor in CTCs prior, during and upon progression in patients with metastatic TNBC treated with ONC201 with a methionine-restricted diet.

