### **8.2 Circulating tumor cells (CTCs)**

If funding is secured, CTCs will be enumerated and evaluated for TRAIL expression. We hypothesize that treatment with MR diet will increase the expression of TRAIL receptors on CTCs and reduce the number of CTCs.

**Time points:** CTCs will be collected at baseline, on day 5 of cycle 2, and at end of treatment. If the CTC sample is not collected at baseline, the remaining samples should not be collected. Missed CTC samples will not be considered a protocol deviation.

Please note that CTC samples must be shipped Monday –Thursdays only. Samples must be shipped to arrive at the [name] lab by Fridays by 12:00 p.m. CTC samples will be drawn only at those sites identified by the coordinating site as having adequate resources (shipping and funding) to provide the samples.

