### 13.7.2 Analysis plans for secondary objectives

PFS and OS will be summarized using Kaplan-Meier estimates of the median survival times. Point estimates as well as 95 % confidence intervals will be provided. PFS based on degree of AR expression by IHC (AR >0% vs. AR  $\geq$ 10%) will be compared using the log-rank test. Additional exploratory analyses using proportional hazards model to control for other factors may be performed.

CBR at 4 months will be estimated according to RECIST 1.1, by dividing the total number of responders (complete plus partial responses plus CR or PR or stable disease (SD)), by number of subjects with measurable disease and the exact 95% confidence interval will be provided. In evaluating CBR, subjects with missing data will be considered non-responders. Also, duration of response (DOR) will be measured using Kaplan-Meier methodology. A 95% confidence interval will be provided for the median duration of response. Subjects who do not relapse will be censored at the day of the last objective tumor assessment. In evaluating response duration, non-responders will be excluded from analysis.

In addition, correlation analyses will be performed to assess the expression of TRAIL receptor in CTCs prior, during and upon progression of disease. Formal statistical tests will be performed based on the outcome types and the biomarker quantification.

Safety and Tolerability by NCI CTCAE v5.0 will be assessed by frequency tables. Also, metabolic indices in patients with metastatic TNBC treated with ONC-201 and a methionine-restricted diet will be assessed by frequency tables and descriptive statistics.

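### The third CTC draw is set 30 to 40 days after the last dose and is not tied to documented progression, so the progression time point of objective 2.2.5 cannot be interpreted

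*Combined protocol and SAP*

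**What the plan says.** Section 2.2.5 sets the objective: "To assess the expression of TRAIL receptor in CTCs prior, during and upon progression in patients with metastatic TNBC". Section 13.7.2 plans correlation analyses "to assess the expression of TRAIL receptor in CTCs prior, during and upon progression of disease".

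Section 8.2 gives the sampling times: "CTCs will be collected at baseline, on day 5 of cycle 2, and at end of treatment". The study schema and calendar footnote 5 (section 7) list the same three draws. The calendar heads the End of Treatment column "35 days from last dose of study treatment +/- 5 days". In that column the ONC201 and diet rows are blank and the CTC row is marked.

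Two further provisions bear on the draws. The footnote to Table 2 (section 5.3) says the diet must be "followed for a minimum of 24 hours prior to the collection of CTCs" and names no exception. Calendar footnote 5 loosens the day 5 timing: "If necessary, these labs may be drawn as early as day 2", with a stated preference for a draw close to day 5.

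**The concern.** The objective names a disease state, but the calendar names a visit counted from the last dose. The two coincide only if progression and the End of Treatment visit coincide, and the calendar's timing keeps them weeks apart.

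This matters because of the trial's own rationale. Section 1.4 reports that methionine deprivation raises TRAIL-R2, and section 8.2 hypothesises that the diet raises receptor expression on CTCs. If expression falls between cycle 2 and a sample taken a month after diet and drug have stopped, the fall could reflect resistance, withdrawal of the exposure that raised expression, or the next treatment. The plan gives no means of telling these apart, yet the result would be reported as expression upon progression.

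**Working it through.** The plan states no figure here to reproduce. The check is date arithmetic on the calendar.

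**Inputs**
- End of Treatment visit: 35 ± 5 days after the last dose (section 7).
- ONC201 half-life at 625 mg: mean 11.3 h, SD 5.2 h (section 1.5.3, Table 1).
- Doses on days 3, 4, 10, 11, 17 and 18 of a 21-day cycle (section 5.2).
- Diet on days 1 to 5 of each week, while taking ONC201 (section 5.3).
- Scans within the 7 days before cycles 4, 7, 10 and so on (calendar footnote 10).

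**1. Time off drug.** Number of half-lives = days × 24 / half-life.
- Mean half-life: 30 × 24 / 11.3 = 64; 35 × 24 / 11.3 = 74; 40 × 24 / 11.3 = 85.
- Half-life 2 SD longer (11.3 + 2 × 5.2 = 21.7 h): 30 × 24 / 21.7 = 33; 40 × 24 / 21.7 = 44.

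Either way, essentially no plasma drug remains.

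**2. Time off diet.** The last weekly dose is on day 4 and the last diet day is day 5, one day later. The draw is therefore 30 − 1 = 29 to 40 − 1 = 39 days after the last diet day. No section says outright that the diet stops at end of treatment. This is inferred from section 5.3 and the blank diet row in that column.

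**3. Lag from the scan that shows progression.** Take the scan before cycle 4, done on cycle 3 days 15 to 21.
- Last dose on day 18: visit on day 18 + 30 = 48 to 18 + 40 = 58. Lag 48 − 21 = 27 to 58 − 15 = 43 days.
- Last dose on day 11: visit on day 41 to 51. Lag 41 − 21 = 20 to 51 − 15 = 36 days.

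**4. Is end of treatment always progression?** No. Section 6.3 also ends protocol therapy for physician judgement, patient request, pregnancy, grade 2 or higher weight loss on the diet, and interruption beyond 21 days. It makes explicit provision for patients who stop before progressing.

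**5. Can new therapy come first?** No section requires the draw to precede it. Section 12.4.1.2 closes its reporting window at 30 days or at the start of new anti-cancer therapy, whichever is earlier, so new therapy inside 30 days is foreseen.

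**6. The cycle 2 draw.**
- Day 2: previous dose on cycle 1 day 18, so 21 + 2 − 18 = 5 days, or 5 × 24 / 11.3 = 10.6 half-lives.
- Day 5: previous dose on day 4, so 1 day, or 24 / 11.3 = 2.1 half-lives.

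Section 13.7.2 does not distinguish the two.

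**The case against.** The other side has real points.

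- **The objective does not ask for an on-treatment sample.** It says upon progression, and progression itself ends therapy. This stands, but a draw some three to six weeks after the scan, possibly after another treatment has started, is still not a progression sample.
- **Moving the draw does not restore exposure.** At a day 1 visit the last dose (day 18) is 22 − 18 = 4 days back, or 4 × 24 / 11.3 = 8.5 half-lives, and the last two days of the previous cycle are off diet. This stands. The gain is a shorter washout and no intervening therapy. It does not give a sample under treatment.
- **Half-lives describe plasma only.** Section 1.5.2 says that Akt and ERK inhibition in cancer cells persists after drug removal. Biological effect may therefore outlast drug, which makes the 35-day sample harder to interpret.

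Some stronger readings are tempting, but the documents do not support them.

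- A reader might infer that the baseline and third draws violate the 24-hour diet rule. Taken literally they cannot meet it. But the rule sits in a footnote about flexibility within the diet week, and the section 8.2 hypothesis needs an off-diet baseline. The rule was plausibly meant for the on-treatment draw. The text needs reconciling, and the samples are not shown to be invalid.
- A reader might infer that a cycle 2 day 2 draw reflects diet alone. It follows six scheduled cycle 1 doses and three diet weeks. It is only a draw before that week's doses.
- A reader might infer that objective 2.2.5 fails altogether. The before-versus-during contrast survives.
- A reader might count all 34 patients as affected. CTC work depends on funding and selected sites, later samples are dropped when baseline is missed, and the trial may stop after 13.

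**Conclusion.** The point holds for the progression component. As scheduled, the third sample is a post-treatment sample: 30 to 40 days off drug, about 29 to 39 days off diet, and 20 to 43 days after the scan in the two examples worked. It comes from a mix of patients with and without progression, some possibly on new therapy. It cannot support a statement about TRAIL-receptor expression upon progression.

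This is a minor point. It concerns one time point of a secondary correlative endpoint that is itself conditional on funding and for which missed samples are not deviations. The primary ORR analysis and the two-stage sample size are not touched.

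The conclusion assumes that the calendar heading governs the CTC draw (no other timing is given), that the diet ends with treatment, and that the dosing and scan days follow the plan. The number of patients affected cannot be derived from the documents.

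**What to change.** 1. In the calendar and section 8.2, move the third CTC tube to the visit where progression is documented or the decision to stop is made, before any new anti-cancer therapy starts. This concerns when the tube is drawn, not when therapy begins.
2. In section 13.7.2, analyse as progression samples only those from patients with documented progression, and report the others separately.
3. If the 35-day draw is kept, label it post-treatment and reword objective 2.2.5 and section 13.7.2 to match.
4. Reconcile the Table 2 footnote with section 8.2 and calendar footnote 5 by stating which draws the 24-hour diet rule covers.
5. Report cycle 2 draws taken before that week's day 3 and 4 doses separately from later ones. Sample dates and times (section 8.4) and the dosing diaries (section 5.3) already allow this.

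The cost is wording in the calendar and in sections 5.3, 8.2 and 13.7.2, with the same number of tubes. The downsides are that one draw is tied to the progression visit and to the Monday to Thursday shipping limit, and that it may still fall several days after the last dose and off diet. Draw timing cannot be repaired after collection, so the change is useful only if made before these samples are taken.
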